2.1 Primary Objectives

- (1) To evaluate the alleviating effect of repetitive transcranial magnetic stimulation (rTMS) on chronic visceral pain in patients with diarrhea-predominant irritable bowel syndrome (IBS-D); (2) To assess the interventional effect of pinaverium bromide and bifidobacterium used alone on

chronic visceral pain in IBS-D; (3) To analyze potential interactions between the two intervention measures.

3. Rationale

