Study Protocol

(Version number: 2.0 Version date: 2025.08.21)

Project Title: Effect of Transcranial Magnetic Stimulation vs Sham Stimulation Combined With Pinaverium Bromide vs Bifidobacteria in Diarrhea-Predominant Irritable Bowel Syndrome: A 2×2 Factorial Randomized Clinical Trial

Sponsor: The First Affiliated Hospital of Soochow University

Responsible Department: Gastroenterology Department

Principal Investigator: [name]

Participating Centers: Xiangcheng People's Hospital of Suzhou, The People's Hospital of Suzhou New District

Investigator Statement and Protocol Signature Page

As the principal investigator of this research project, I hereby commit to adhering to the ethical principles outlined in the National Health Commission's "Ethical Review Measures for Biomedical Research Involving Humans" (2016), the WMA's "Declaration of Helsinki" (2013), the CIOMS's "International Ethical Guidelines for Biomedical Research Involving Human Subjects" (2002), and Good Clinical Practice (GCP). Under the guidance of the Quality Management Standards for Drug Clinical Trials, I will implement the study protocol approved by the Ethics Committee and conduct the research in strict accordance with the requirements of this protocol, ensuring the scientific validity of the study and protecting the health and rights of the subjects.

Name: [name]

Signature:

Date:2025.07.01

Protocol Synopsis

Study objective	(1) To evaluate the alleviating effect of repetitive transcranial magnetic stimulation (rTMS) on chronic visceral pain in patients with diarrhea-predominant irritable bowel syndrome (IBS-D); (2) To assess the interventional effect of pinaverium bromide and bifidobacterium used alone on chronic visceral pain in IBS-D; (3) To analyze potential interactions between the two intervention measures.
Sample size	140
Study population	Patients with diarrhea-predominant irritable bowel syndrome
Study design	Randomized, controlled factorial design study
Inclusion criteria	(1) Age range 18-75 years (either sex) (2) Fulfilling the Rome IV criteria for irritable bowel syndrome diagnosis (3) Bristol stool type 6-7 in >25% and type 1-2 in <25% of bowel movements (4) Patients experienced Bristol stool type 6 or 7 on ≥ 4 days with mean abdominal pain score ≥ 3 during the initial 2-week period

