Exclusion criteria	(1) Documented organic gastrointestinal pathology; endocrinologic or metabolic diseases with known gastrointestinal motility effects including diabetes mellitus and hyperthyroidism; previous surgical interventions involving abdominal cavity intestinal tract or anal region (2) current use of any medication with documented effects on gastrointestinal motility or secretory function; administration of concurrent therapies or pharmacologic agents capable of confounding treatment efficacy or safety evaluations (3) pregnancy lactation or postpartum status within 12

	
months
 
(4) noncompliance with randomized treatment allocation or demonstrated poor adherence tendencies

Intervention	
(1) IBS patients receiving rTMS stimulation + pinaverium bromide treatment
 
rTMS stimulation: 1 Hz, 80% MT, 20 min/d, once daily for 2 weeks;
 
Pinaverium bromide: Oral, 3 times daily, 1 tablet/time, for 2 weeks;
 
(2) IBS patients receiving rTMS stimulation + bifidobacterium treatment
 
rTMS stimulation: 1 Hz, 80% MT, 20 min/d, once daily for 2 weeks;
 
Bifidobacterium: Oral, 2 times daily, 4 capsules/time, for 2 weeks;
 
(3) IBS patients receiving sham rTMS + pinaverium bromide treatment
 
Sham rTMS treatment: 0 Hz, 0% MT, 20 min/d, once daily for 2 weeks;
 
Pinaverium bromide: Oral, 3 times daily, 1 tablet/time, for 2 weeks;
 
(4) IBS patients receiving sham rTMS + bifidobacterium treatment
 
Sham rTMS stimulation: 0 Hz, 0% MT, 20 min/d, once daily for 2 weeks;
 
Bifidobacterium: Oral, 2 times daily, 4 capsules/time, for 2 weeks;

Primary endpoint	The primary outcome measure is the proportion of patients achieving a composite response at the end of treatment

	(Week 2), defined as: a reduction of $\geq 30\%$ from baseline in the average daily worst abdominal pain score, and a reduction of $\geq 50\%$ in the number of days with at least one stool consistency meeting BSFS type 6 or 7 criteria during Week 2. Abdominal pain intensity is assessed using an 11-point NRS scale (0-10) for the last 24 hours daily. Stool consistency is recorded daily by the patient selecting the most representative category according to the BSFS.

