Dropout Rate (DR) is the percentage of subjects (or items) that are expected to be lost at random during the course of the study and for whom no response data will be collected (i.e., will be treated as "missing"). N1, N2, and N are the evaluable sample sizes at which power is computed. If N1 and N2 subjects are evaluated out of the N1' and N2' subjects that are enrolled in the study, the design will achieve the stated power. N1', N2', and N' are the number of subjects that should be enrolled in the study in order to end up with N1, N2, and N evaluable subjects, based on the assumed dropout rate. After solving for N1 and N2, N1' and N2' are calculated by inflating N1 and N2 using the formulas N1' = N1 / (1 - DR) and N2' = N2 / (1 - DR), with N1' and N2' always rounded up. (See Julius, S.A. (2010) pages 52-53, or Chow, S.C., Shao, J., Wang, H., and Lokhnygina, Y. (2018) pages 32-33.) D1, D2, and D are the expected number of dropouts. D1 = N1' - N1, D2 = N2' - N2, and D = D1 + D2.

Procedure Input Settings

Autosave Inactive

Design Tab

Solve For:	Sample Size
Power Calculation Method:	Normal Approximation
Alternative Hypothesis:	Two-Sided
Test Type:	Z-Test (Pooled)
Power:	0.80
Alpha:	0.05
Group Allocation:	Equal (N1 = N2)
Input Type:	Proportions
P1 (Group 1 Proportion H1):	0.476190476
P2 (Group 2 Proportion):	0.238095238

5. Detailed Study Content

5.1 Overall Study Design:

Project Title: The Effect of Repetitive Transcranial Magnetic Stimulation Combined with Pinaverium Bromide or Bifidobacterium versus Sham Stimulation on Chronic Visceral Pain in Patients with Diarrhea-Predominant Irritable Bowel Syndrome: A Randomized, Controlled Factorial Design Study

Study Type: Prospective 2*2 factorial designed randomized controlled study

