This is a multicenter, prospective, 2*2 factorial designed randomized controlled study¹⁹ evaluating the effectiveness of TMS for treating irritable bowel syndrome. This study will recruit and screen subjects according to ethical review standards. Subjects will be randomly divided into an rTMS stimulation + pinaverium bromide treatment group, an rTMS stimulation + bifidobacterium treatment group, a pinaverium bromide + sham rTMS treatment group, and a bifidobacterium + sham rTMS stimulation group for clinical trials. Pain and stool characteristics will be assessed after 2 weeks of treatment, and data will be collected and analyzed finally. This study aims to deeply explore the clinical efficacy of Transcranial Magnetic Stimulation (TMS) on chronic visceral pain in patients with Irritable Bowel Syndrome (IBS), in order to provide more reliable and effective therapeutic targets for clinical application.

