5.2 Subject Grouping

Intervention measures (Including whether the investigational drugs are used off-label. If used

off-label, the safety and necessity of the research must be justified, and the off-label use must be detailed in the informed consent form.)

(1) IBS-D patients receiving rTMS stimulation + pinaverium bromide treatment

rTMS stimulation: 1 Hz, 80% MT, 20 min/d, once daily for 2 weeks;

Pinaverium bromide: Oral, 3 times daily, 1 tablet/time, for 2 weeks;

(2) IBS-D patients receiving rTMS stimulation + bifidobacterium treatment

rTMS stimulation: 1 Hz, 80% MT, 20 min/d, once daily for 2 weeks;

Probiotic: Oral, 2 times daily, 4 capsules/time, for 2 weeks;

(3) IBS-D patients receiving Sham rTMS stimulation + pinaverium bromide treatment

Sham rTMS treatment: 0 Hz, 0% MT, 20 min/d, once daily for 2 weeks;

Pinaverium bromide: Oral, 3 times daily, 1 tablet/time, for 2 weeks;

(4) IBS-D patients receiving Sham rTMS stimulation + bifidobacterium

Sham rTMS stimulation: 0 Hz, 0% MT, 20 min/d, once daily for 2 weeks;

Probiotic: Oral, 2 times daily, 4 capsules/time, for 2 weeks;

Dose Selection/Adjustment

rTMS stimulation: 1 Hz, 80% MT, 20 min/d, once daily for 2 weeks;

Pinaverium bromide: Oral, 3 times daily, 1 tablet/time, for 2 weeks;

Probiotic: Oral, 2 times daily, 4 capsules/time, for 2 weeks;

Administration Time

This study adopts a standardized administration time scheme to ensure treatment consistency:

Pinaverium bromide (50mg) is taken orally 30 minutes before meals three times daily,

Bifidobacterium (500mg) is taken after breakfast and before bedtime, both study drugs are

dispensed with electronic medication boxes (MediSafe system) for timed reminders and

medication recording.

Blinding/Unblinding

Blinding method: rTMS real/sham stimulation uses identical equipment and operating sounds, administered by an independent technician through an encrypted control system; drugs (pinaverium bromide/bifidobacterium) use matching placebos (identical capsules, boxes, labels),

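### Primary objective 2 promises the effect of each drug on its own, but every arm contains one of the two drugs, so the only randomised drug contrast is pinaverium versus bifidobacterium

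*Protocol*

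**What the plan says.** The synopsis and section 2.1 give three objectives, which section 2.1 classes as primary. The second is "To assess the interventional effect of pinaverium bromide and bifidobacterium used alone", with chronic visceral pain as the target. The third is "To analyze potential interactions between the two intervention measures".

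The arms are the same in the synopsis, 5.1 and 5.2: rTMS with pinaverium, rTMS with bifidobacterium, sham with pinaverium, sham with bifidobacterium. The synopsis describes the third as "IBS patients receiving sham rTMS + pinaverium bromide treatment". Section 5.1 names the two sham groups as "a pinaverium bromide + sham rTMS treatment group, and a bifidobacterium + sham rTMS stimulation group".

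Drug placebos appear once, under Blinding/Unblinding in 5.2: "drugs (pinaverium bromide/bifidobacterium) use matching placebos (identical capsules, boxes, labels". No arm is defined by them.

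The cover title sets the drugs against each other: "Sham Stimulation Combined With Pinaverium Bromide vs Bifidobacteria in Diarrhea-Predominant Irritable Bowel Syndrome".

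The sample size in section 4 is built on rTMS alone, at 47.6% against 23.8%, with 63 per group and 140 patients after 10% dropout.

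**The concern.** An effect of a drug needs a comparison with patients who do not receive it, and who receive either nothing or a placebo in its place. No arm here meets that description: each drug's only randomised comparator is the other drug. A stated primary objective thus asks for a quantity that the arms cannot supply. This follows from the arms, so an analysis plan that is not shown could not repair it.

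Two misreadings are at stake. The response rate or change from baseline in a sham arm could be taken as the effect of the drug in that arm. And if pinaverium and bifidobacterium come out alike, the result could be read as both working or as neither working, which the trial cannot tell apart.

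**Working it through.** **1. What the four arms identify.** Let m be the mean under sham with no drug, t the rTMS effect, p the pinaverium effect and b the bifidobacterium effect. In an additive model the arm means are:

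- rTMS + pinaverium: m + t + p
- rTMS + bifidobacterium: m + t + b
- sham + pinaverium: m + p
- sham + bifidobacterium: m + b

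Add any constant to both p and b and subtract it from m: all four arm means stay the same. The data therefore cannot fix p or b. The design matrix has rank 3 for 4 parameters. A row-space check gives:

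- t: estimable
- p − b: estimable
- p alone, b alone: not estimable

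With rTMS-by-drug terms added, p and b are still not estimable, while p − b within sham and the interaction contrast are. This is a formal restatement of the fact that 0 of 4 arms are drug-free; it is not separate evidence.

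**2. The reading as drug plus sham.** The arms in question are the third and fourth. Between them the randomised contrast is (m + p) − (m + b) = p − b, again one drug against the other. Within one of them, the change from baseline combines the drug effect with placebo response and regression to the mean. The last is a real possibility, because section 3.2 selects patients on a mean pain score of at least 3 and at least 4 diarrhoeal days in the run-in, and the endpoint is measured as change from baseline.

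**3. The protocol's own sample size.** Inputs from section 4: rates 10/21 = 0.4762 and 5/21 = 0.2381, two-sided alpha 0.05, power 0.80, pooled Z-test.

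- Mean rate 0.3571; √(2 × 0.3571 × 0.6429) = 0.6776
- √(0.2381 × 0.7619 + 0.4762 × 0.5238) = √0.4308 = 0.6564
- n = (1.960 × 0.6776 + 0.8416 × 0.6564)² / 0.2381² = 3.537 / 0.0567 = 62.4, so 63 per group
- 126 / 0.9 = 140

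The stated figures reproduce (power at 63 per group is 0.804). They concern rTMS and are used below only for the 126 evaluable patients.

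**4. Precision of the drug contrast that can be estimated.** Assumptions: equal allocation over four arms (the four-arm ratio is not stated) and rates of 23.8% and 47.6%, borrowed from section 4 for illustration. Wald 95% half-width = 1.96 × √(p₁(1 − p₁)/n₁ + p₂(1 − p₂)/n₂).

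- Pooled over stimulation, 63 vs 63: 1.96 × √(0.1814/63 + 0.2494/63) = 1.96 × 0.0827 = 0.162
- Within sham, 31 vs 32: 1.96 × √(0.1814/31 + 0.2494/32) = 1.96 × 0.1168 = 0.229

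The assumed rates matter little. With 23.8% on both drugs the half-widths are 1.96 × √(2 × 0.1814/63) = 0.149 and 1.96 × √(0.1814 × (1/31 + 1/32)) = 0.210. At the widest case, 50% on both, they are 1.96 × √(0.5/63) = 0.175 and 1.96 × √(0.25 × (1/31 + 1/32)) = 0.247.

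**The case against.** The best defence is that objective 2 names no comparator. In a trial whose other factor is rTMS, a drug used alone can naturally mean without active rTMS, and section 3.4 contrasts a combination group with single-drug groups. Read with the cover title, the objective then becomes pinaverium versus bifidobacterium under sham, which is answerable and only loosely worded. This reading is fair, and it means that objective 2 should not be called unanswerable in every sense. But it leads to the same drug-versus-drug contrast, and the objective as written still speaks of the effect of the drugs rather than of a difference between them.

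A reader might infer more than the documents support:

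- **That the 5.1 title contradicts the cover title.** Its words "Combined with Pinaverium Bromide or Bifidobacterium versus Sham Stimulation on Chronic Visceral Pain" look like drugs set against sham, but the phrase begins with rTMS. Read in full, it states the stimulation contrast and is silent on the drug contrast.
- **That objective 3 miscounts the interventions.** Two measures is correct for a 2×2 factorial, with the drugs forming one factor.
- **That the trial is underpowered for the drug question.** The protocol makes no power claim for it, and the rTMS difference cannot simply be carried over to two active drugs. Precision is the safer statement.
- **That the 23.8% has no source.** Section 4 attributes its assumptions to earlier literature and a preliminary trial. All that can be said is that it calls this a placebo rate while its control patients receive sham plus an active drug.

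**Conclusion.** The point holds, and objective 2 should be corrected. One of three primary objectives promises an effect that the arms cannot deliver: no arm is free of active drug, and the matching placebos do not create one. Pinaverium versus bifidobacterium can be estimated with a half-width of about 16 points pooled (15 to 17 over the rates tried) or 23 points within sham (21 to 25). Those figures rest on equal four-arm allocation and 126 evaluable patients; the main conclusion rests on neither.

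The finding does not touch the rTMS comparison or the interaction, and it is no judgement on the total of 140. Nor does it show that a sham-arm result will be misreported, only that the present wording invites it.

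**What to change.** In the synopsis and section 2.1, restate objective 2 as a comparison of pinaverium bromide with bifidobacterium, in line with the cover title. Say whether it is pooled over stimulation or made within sham. The pooled version includes patients on active rTMS; the within-sham version is closer to the present wording but uses half the patients, and its lower precision should be acknowledged.

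Add a sentence that the trial gives no placebo-controlled estimate for either drug, so that a null difference cannot be read as both drugs working or neither working. Optionally, note in section 4 that the group assigned the 23.8% rate receives sham plus an active drug.

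The cost is wording and a narrower drug claim. Arms, endpoint and N are unchanged.

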3.1 Preclinical Animal Experiments and Literature Basis

The mechanisms underlying chronic visceral pain in IBS are complex. The ascending transmission of nociceptive signals primarily involves peripheral noxious information being transmitted via primary sensory neurons to the dorsal horn of the spinal cord, where it is integrated and relayed further to the brain. Current mechanistic research on chronic visceral pain in IBS primarily focuses on the peripheral primary sensory neurons and central brain levels⁶. Studies on the central sensitization mechanism of visceral pain include alterations in neuronal excitability in pain-related brain regions, changes in synaptic transmission, and abnormalities in neural circuit function. Our previous collaborative research with [name] team at the Institute of Neuroscience, Soochow University, demonstrated that adverse neonatal stimuli (such as maternal deprivation) lead to increased neuronal excitability in the insular cortex and enhanced function of the claustrum–anterior cingulate cortex (ACC) neural circuit, thereby inducing chronic visceral pain⁷. These findings suggest that the central nervous system plays a critical role in the pathophysiology of chronic visceral pain in IBS. In the first part of our foundational study, using an animal model simulating chronic visceral pain in IBS, we found that the glutamatergic neural circuit between the ACC and medial prefrontal cortex (mPFC) is involved in the development and persistence of chronic visceral pain, indicating that this circuit may be a key mechanism regulating chronic visceral pain in IBS. These results not only reveal the neural circuit mechanisms underlying central sensitization in chronic visceral pain but also provide new evidence for the regulatory role of the central nervous system in the pathophysiology of IBS. Based on this research, the critical role of the central nervous system in IBS-related chronic visceral pain has become increasingly clear, providing an important theoretical foundation for developing treatments targeting the central nervous system.

However, current treatment strategies for chronic visceral pain in IBS predominantly focus on peripheral interventions, such as pharmacological, psychological, and dietary modifications.

Although these approaches can provide temporary symptomatic relief, they are limited by unstable efficacy and significant side effects⁸. Therefore, there is an urgent need to explore treatments that target the central nervous system, offering holistic regulation, greater safety and efficacy, and fewer side effects. Central neuromodulation, as an emerging therapeutic strategy, holds promise for breakthroughs in treating chronic visceral pain in IBS by directly modulating pain-related neural circuits and brain functions. In particular, the rapid advancement of neuromodulation technologies in recent years has attracted widespread attention in the field of chronic pain management. Among these, repetitive transcranial magnetic stimulation (rTMS) has become a research focus due to its non-invasive, painless, and safe profile⁹. rTMS delivers repeated magnetic stimuli via an electromagnetic coil placed on the head, transferring energy to brain tissue to generate electric currents that modulate neuronal excitability and cerebral metabolism, thereby achieving therapeutic effects. Since its introduction, rTMS has been widely used to treat neurological and psychiatric disorders. The 2014 rTMS treatment guidelines indicate¹⁰ that rTMS can be used to treat various conditions, including pathological pain, movement disorders, disorders of consciousness, tinnitus, depression, and anxiety disorders. Previous studies have shown that rTMS can directly excite the thalamus via corticothalamic projections, inhibiting the transmission of sensory information through the spinothalamic tract, thereby alleviating abdominal pain in patients with chronic pancreatitis¹¹. However, research on whether rTMS can alleviate chronic visceral pain in IBS patients remains limited^{12,13}, and the specific mechanisms of rTMS intervention in IBS-related chronic visceral pain are not yet fully understood. Based on our previous findings, the ACC-mPFC glutamatergic neural circuit may play a key role in the development and persistence of chronic visceral pain in IBS¹⁴⁻¹⁷, leading us to a new research question: Could rTMS, by modulating excitability in the mPFC and influencing the ACC-mPFC glutamatergic circuit, become a novel intervention for chronic visceral pain in IBS patients? This question warrants in-depth investigation.

Therefore, this study aims to explore the efficacy of rTMS intervention for chronic visceral pain in IBS, seeking to elucidate the specific mechanisms by which rTMS alleviates chronic visceral pain through modulation of pain-related neural activity (e.g., in the mPFC) and neural network interactions (e.g., the ACC-mPFC circuit). This research will not only provide central evidence

supporting the clinical effects of rTMS for chronic visceral pain in IBS but also establish an experimental foundation for future clinical applications.

3.2 Subject Selection Rationale

This study selects patients who meet the Rome IV diagnostic criteria for irritable bowel syndrome, with Bristol Stool Form Scale types 6-7 accounting for >25% of bowel movements, and hard/lumpy stools (types 1-2) accounting for <25%. Age range is between 18-75 years. During the 2-week run-in period, the patient has at least 4 days with diarrheal stools (Bristol Stool Form Scale type 6 or 7), and an average abdominal pain intensity ≥ 3 points (based on a 0 to 10 point Numerical Rating Scale [NRS]).

3.3 Endpoint Selection Rationale

The primary outcome measure is the proportion of patients achieving a composite response at the end of treatment (Week 2), defined as: a reduction of $\geq 30\%$ from baseline in the average daily worst abdominal pain score, AND a reduction of $\geq 50\%$ in the number of days with at least one stool consistency meeting BSFS type 6 or 7 criteria during Week 2. Abdominal pain intensity is assessed using an 11-point NRS scale (0-10) for the last 24 hours daily. Stool consistency is recorded daily by the patient selecting the most representative category according to the BSFS.

